11.6 Regulatory Reporting to the Health Authorities

Expedited reporting of SAEs and non-serious ADRs to Health Authorities is performed by the Sponsor's Local Patient Safety Officer according to applicable global and local requirements.

In addition, the investigator will comply with any applicable local pharmacovigilance requirements to report appropriate safety data, to national pharmacovigilance systems (e.g. Yellow Card Scheme in the United Kingdom), as required by country specific reporting requirements.

12 Plans for Disseminating and Communicating Study Results

12.1 Study Report

The first and second interim reports will present the results of analyses of the safety, adherence, and PRO data. These reports will allow interim assessment of the safety of cladribine tablets in this study.

The third interim report will present results of the analysis of the safety, adherence, and PRO data, as well as the analyses of the primary and secondary outcomes at 12 months. This report will allow interim assessment of all relevant aspects of the study.

The completed study will be summarized in a final clinical study report that accurately and completely presents the study objectives, methods, results, limitations of the study, and interpretation of the findings from study start through Month 24.

## 2 List of Abbreviations and Definition of Terms

ADR	Adverse Drug Reaction
AE	Adverse Event
AESI	Adverse Event of Special Interest
ALC	Absolute Lymphocyte Count
ARR	Annualized Relapse Rate
aSPMS	active Secondary Progressive Multiple Sclerosis
ATC	Anatomical Therapeutic Chemical Classification
BDI-FS	Beck-Depression Inventory - Fast Screen
BMI	Body Mass Index
CI	Confidence Interval
CIS	Clinically Isolated Syndrome
CSR	Clinical Study Report
CTCAE	Common Terminology Criteria for Adverse Event
CU	Combined Unique
DMD	Disease-Modifying Drug
eCRF	Electronic Case Report Form
ePRO	Electronic Patient-Reported Outcome
FAS	Full Analysis Set
Gd+	Gadolinium-Enhancing
GENMOD	Generalized Linear Model
HIV	Human Immunodeficiency Virus
IAP	Integrated Analysis Plan
JCV	John Cunningham Virus
KM	Kaplan-Meier
MCS	Mental Component Summary Score
MedDRA	Medical Dictionary for Regulatory Activities
MH	Mental Health
MFIS-5	Modified Fatigue Impact Scale – 5-Item Version
MRI	Magnetic Resonance Imaging
MS	Multiple Sclerosis

MS-TAQ	Multiple Sclerosis Treatment Adherence Questionnaire
NB	Negative Binomial
PCS	Physical Components Summary Score
PDDS	Patient Determined Disease Steps
PF	Physical Function
PP	Per Protocol Analysis Set
PPMS	Primary Progressive Multiple Sclerosis
PRO	Patient-Reported Outcomes
РТ	Preferred Term
RMS	Relapsing form of Multiple Sclerosis
RRMS	Relapsing-Remitting Multiple Sclerosis
SAE	Serious Adverse Events
SAF	Safety Analysis Set
SAS	Statistical Analysis System
SD	Standard Deviation
SF	Short Form Health Survey
SOC	System Organ Class
TEAE	Treatment-Emergent Adverse Events
TSQM	Treatment Satisfaction Questionnaire for Medication
USPI	United States Product Information
WHO-DD	WHO-Drug Dictionary
WPAI-MS	Work Productivity Activity Impairment – MS

## 3 Modification History

Unique Identifier for Version	Date of IAP Version	Author	Changes from the Previous Version
1.0	11 July 2019	PPD	Not Applicable
2.0 Draft	07 April 2020	PPD	Updated for the use of the Optum software for the derivation of the composite scores of the SF36 questionnaire
			Updated to replace 'enrolment visit' with 'baseline visit'
			Time window for MS-TAQ questionnaire during the study updated from ±30 days to ±15 days
			Section 14.1.1 updated to highlight that the last available date of a patient will be used in the Interim Analyses to determine the Time on Study and ARR
			Updated to use the correct version of the SF 36 questionnaire
			Updated section 9, General Specifications for Data Analyses, to take into account the Handling of partially missing dates
			Updated section 13 giving a definition of treatment compliance
			Section 14.1.4: the description of the multiple imputation analysis of the primary endpoint has been extended
2.0 Final	08 February 2022	PPD	
 
Updated after CTP amendment 7.0 to:         
 
Analyze the 2-year Safety extension period. Throughout the document, months "48" and "48/54" both refer to the original 24-month study plus the 24-month Safety extension
 
Nomenclature updated per CTP amendment: "Subject" replaced by "Patient"
 
 
 

3.0 Final	08 February 2023	PPD	Section 6.6 update to clarify which is the first day of the safety extension period and to clarify that only patients who started the Year 2 treatment will be included in the safety extension analysis.
			Section 8.2 updated to clarify the definition of the Per Protocol Analysis Set and the Safety Extension Analysis Set (MRI removed from the derivation).
			Section 9 updated to remove the analysis window for exposure data, PDDS and MS-TAQ. The definition of the analysis window

Unique Identifier for Version	Date of IAP Version	Author	Changes from the Previous Version
			for the other PROs has been updated to consider the correct months.
			Section 9 updated to ensure that the imputation of the partial date for the last DMD is always before the date of first dose of cladribine.
			In Section 9 the following sentence has been removed since it is not related to specifications for the analysis: 'the last assessment of the safety extension, Visit 10, will be considered missing if not recorded within 30 days of the last planned assessment.'
			Section 10.1 updated to clarify that the number of patients included in the SAFX will be presented.
			Section 13 updated by adding the definition for the date of discontinuation of cladribine tablets.
			In Section 14.2 the analysis of MRI data during the safety extension period has been removed.
4.0 Final	xx xxx 2024	PPD	Removed 2-year safety extension related texts from abbreviations, paragraphs, tables, footnotes, and affiliated data collection items and timepoints. The updated sections are as follows: Sections 2, 4, 5, 6, 6.6 (sections removed), 8.2, 13, 14, 2, 15, 15, 1, and 16, 3

## 4 **Purpose of the Integrated Analysis Plan**

The purpose of this Integrated Analysis Plan (IAP) is to document technical and detailed specifications for the final analysis and interim analyses, of data collected for protocol MS700568\_0078. Results of the analyses described in this IAP will be included in the Clinical Study Report (CSR). Additionally, the planned analyses identified in this IAP may be included in regulatory submissions or future manuscripts. Any post-hoc, or unplanned analyses performed to provide results for inclusion in the CSR but not identified in this prospective IAP will be clearly identified in the CSR.

The IAP is based upon section 9.7 (Data Analysis) of the study protocol and protocol amendments and is prepared in compliance with International Conference on Harmonization (ICH) E9. It describes analyses planned in the protocol and protocol amendments.

## 5 **Objectives and Endpoints**

Objectives	Endpoints (Outcome Measures)	Endpoints (Outcome Measures) Timeframe	IAP section
Primary			
To estimate the annualized relapse rate (ARR) over a 24- month period in patients with Relapsing form of Multiple Sclerosis (RMS), including relapsing-remitting multiple sclerosis (RRMS) and active secondary progressive multiple sclerosis (aSPMS), who are treated with cladribine tablets in a real- world setting and after suboptimal response to any injectable Disease-Modifying Drug (DMD) approved in the US for RMS	ARR over 24 months of treatment with cladribine tablets (prospectively collected data)	24-month period from first dose of cladribine tablets (or 30 months if Year 2 treatment is delayed)	Section 14.1
Secondary			
To assess Patient-Reported Outcomes (PROs) and treatment adherence and treatment satisfaction during treatment with cladribine tablets	
 
Baseline scores, scores at the timepoints and change in scores from Baseline to timepoints (Month 6, 12 and 24) for the following PROs (collected via electronic PRO [ePRO] at the practice or at the patient's home): 
 
14-Item Treatment Satisfaction Questionnaire for Medication (TSQM)
 
36-Item Short Form Health Survey (SF-36)
 
Modified Fatigue Impact Scale – 5-item version (MFIS-5)
 
Beck-Depression Inventory – Fast Screen (BDI-FS) (7 items)
 
Work Productivity Activity Impairment – MS (WPAI-MS) (6 items)
 
Patient Determined Disease Steps (PDDS) scale
 
 
 
Treatment adherence based on modified versions of the MS-TAQ; data to be collected via ePRO at Baseline (modified Self-Injectables Version to assess adherence during last previous injectable DMD treatment, only baseline scores) and at the end of Months 1, 2, 13, and 14 (modified for cladribine tablets, only scores at the different time points)
 
	24-month period from enrolment Timepoints for TSQM, SF-36, MFIS-5, BDI-FS, WPAI-MS and PDDS: Baseline, months 6, 12 and 24 (or 30 months if Year 2 treatment is delayed) Adherence assessment timepoints: Baseline (adherence to previous DMD), Months 1, 2, 13, 14 (adherence to cladribine)	Section 16.3 and section 16.4

Objectives	Endpoints (Outcome Measures)	Endpoints (Outcome Measures) Timeframe	IAP section
Other relapse analyses	Proportion of patients experiencing a relapse (24-month and 12-month periods) and ARR over the 12-month period	24-month treatment period (or 30 months if Year 2 treatment is delayed) and 12-month	Section 14.2
	Proportion of patients with relapse associated with hospitalization and ARR associated with hospitalization		
	Proportion of patients with relapse associated with glucocorticoid use and ARR associated with glucocorticoid use	from first dose of cladribine tablets	
To assess treatment patterns (Multiple Sclerosis [MS] treatment prior to transition to cladribine tablets, since MS diagnosis, concomitant treatment for MS during the last 2 years prior to initiation of cladribine tablets (or since MS diagnosis if diagnosis <24 months), follow-up treatment in case of discontinuation of cladribine tablets)	
 
Assessment of previous treatment for MS:         
 
Previous DMD received for MS during the last 2 years
 
Number of previous DMD received for MS (a) during the last 2 years and (b) in total
 
Reasons for discontinuation of last previous DMD
 
 
 
Assessment of concomitant MS medications used during the study period
 
Proportion of patients who discontinue cladribine tablets         
 
Reason for discontinuation of cladribine tablets
 
Elapsed time to discontinuation after the first dose of cladribine tablets
 
Number of doses and % of planned doses of cladribine tablets aproduct Information [USPI]) received
 
 
 
Subsequent treatment chosen following discontinuation of cladribine tablets
 
	For previous treatment: 24- month period prior to initiation of cladribine tablets For concomitant medication, cladribine tablets discontinuation and subsequent treatment: 24- month period from first dose of cladribine tablets (or 30 months if Year 2 treatment is delayed)	Section 11.3 and section 12
To estimate the ARR over the 24-month period prior to initiation of cladribine tablets (or since MS diagnosis if diagnosis <24 months)	The ARR based on the last 24 months prior to the start of treatment with cladribine tablets (or since MS diagnosis if diagnosis <24 months) (retrospective data)	24-month period prior to initiation of cladribine tablets (or since MS diagnosis if diagnosis <24 months)	Section 11.3

Objectives	Endpoints (Outcome Measures)	Endpoints (Outcome Measures) Timeframe	IAP section
To collect all serious adverse events (SAEs), adverse drug reactions (ADRs), adverse events of special interest (AESIs) and special situations during treatment with cladribine tablets over a 24-month period	SAEs, ADRs, AESIs	Adverse event (AE) collected from signed Informed Consent Form (ICF); Treatment- Emergent Adverse Events (TEAEs) considered after first treatment administration through the 24- month treatment period (or 30 months if Year 2 treatment is delayed)	Section 15
CCI			

## 6 Overview of Planned Analyses

There will be a baseline analysis, 3 interim analyses and a final analysis. Baseline and interim analyses are descriptive and for monitoring purposes. Multiplicity corrections will not be considered. Statistical analyses will be performed using the Electronic Case Report Form (eCRF) data gained until the cutoff dates described in the following subsections.

If the start of cladribine Year 2 treatment needs to be delayed (e.g., to allow for lymphocyte recovery to at least 800 cells per microliter), all Year 2 visits and procedures will be moved out accordingly (at most 6 months). If recovery to 800 cells/mL is not complete after the 6-month delay, Year 2 treatment should not be initiated; the patient will nonetheless be followed up until the end of the observation period.

## 6.1 First Interim Analysis

In the first interim analysis, safety, adherence and PRO data will be analyzed for the subset of the first 30 patients enrolled into the study after they have completed the 6-month timepoint. This analysis will be conducted primarily for evaluation of safety.

All safety data (AEs) and hematology data, including JCV status, lymphocyte subtype data, as available) will be evaluated descriptively. Treatment adherence will be evaluated on the basis of the modified versions of the MS-TAQ (at baseline modified Self-Injectables Version to assess adherence during last previous injectable DMD treatment; at Month 1 and Month 2 modified for cladribine tablets). For each PRO score (TSQM, called also TSQM-14), SF-36, MFIS-5, BDI-FS, WPAI-MS, and PDDS), the actual value at each visit and change in scores from Baseline to Month 6 will be described.

## 6.2 Baseline Interim Analysis

The baseline analysis will summarize the patient's baseline characteristics. It will be carried out when the baseline data collected on all patients are available.

Baseline characteristics of patients initiating cladribine tablets, including demographics, baseline PRO data, baseline laboratory data, baseline data on previous MS DMD use, relapses during the previous 2 years (or since MS diagnosis if diagnosis <24 months), baseline MRI data and past treatment adherence will be analyzed.

## 6.3 Second Interim Analysis

In the second interim analysis, safety, adherence and PRO data will be analyzed as soon as 6-month data are available for all patients. This analysis will allow the interim assessment of the safety of cladribine tablets in this study.

The same endpoints as the first interim analysis will be used.

## 6.4 Third Interim Analysis

The third interim analysis will be performed on the 12-month data for all patients.

This analysis will include all the endpoint analyses related to the objectives of the study. For the PROs the actual value at each visit and change in scores from Baseline to Month 6 and 12 will be considered. This analysis will allow the interim assessment of all relevant aspects of the study.

## 6.5 Final Analysis

The final analysis will be performed on the 24-month data for all patients at the end of the study. The corresponding cutoff for the original protocol analysis is forecasted to be in June 2024.

The final analysis will include all the endpoint analyses related to the objectives of the study. For the PROs the actual value at each visit and change in scores from Baseline to Month 6, 12 and 24 will be considered. A comparison of the characteristics of patients completing the study vs. those who drop out will be conducted as well.

## 7 Changes to the Planned Analyses in the Clinical Study Protocol

There are no changes to the planned analyses.

## 8 **Protocol Deviations and Analysis Populations**

### 8.1 Definition of Protocol Deviations and Analysis Populations

Important protocol deviations are protocol deviations that might significantly affect the completeness, accuracy, and/or reliability of the study data or that might significantly affect a patient's rights, safety, or well-being.

Important protocol deviations include:

- Patients that are enrolled in the study despite not satisfying the inclusion/exclusion criteria
- Patients that no longer meet the inclusion/exclusion criteria while on the study but are not withdrawn (e.g., patients may have withdrawn consent)

The following deviations will be identified and confirmed prior to or at the Data Review Meeting at the latest.

Important protocol deviations include:

- Deviations from the inclusion and exclusion criteria
- Deviations post inclusion
- The subset of these important protocol deviations that are clinically important, i.e., leading to the exclusion of a patient from an analysis population (see section 8.2)

All important protocol deviations will be documented in Standard Data Tabulation Model datasets whether identified through site monitoring, medical review or programming.

## 8.2 Definition of Analysis Populations and Subgroups

#### Full Analysis Set (FAS)

The FAS includes all patients enrolled in the study who received at least 1 dose of cladribine tablets.

#### Per Protocol Analysis Set (PP)

The PP includes all patients who have completed a full treatment course of cladribine tablets (2 weeks of treatment [4-5 doses per week] for Years 1 and 2), according to the USPI and are compliant with all entry criteria and without protocol deviations.

If the Per Protocol analysis population includes at least 90% of patients in the FAS analysis population, additional efficacy analyses on the Per Protocol analysis population will be omitted as the differences in the results based upon these 2 analysis populations are expected to be negligible.

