9.2.2 Definition of Study Cohorts and Description of Treatments

The study will have a single cohort that consists of all patients enrolled in the study who received at least 1 dose of cladribine tablets. All treatment and other medical decisions will be made by the investigator.

All study patients are anticipated to receive marketed cladribine tablets as per investigator discretion and as per US approved label: 3.5 mg/kg body weight over 2 years, administered as 1 treatment course of 1.75 mg/kg per year. Each treatment course consists of 2 treatment weeks, 1 at the beginning of the first month and 1 at the beginning of the second month of the respective year. Each treatment week consists of 4 or 5 days on which a patient receives 10 mg or 20 mg (1 or 2 tablets) as a single daily dose, depending on body weight. Since prescribing is determined by the investigator as per standard of care and according to the USPI, the benefits and risks to patients in being in the study are not different than the benefits and risks to patients taking cladribine tablets as per standard of care and according to the USPI in the general population.

Following completion of the 2 treatment courses, do not administer treatment during the next 2 years as stated in the USPI.

As per USPI, ALC values need to be normal at the initiation of cladribine tablets in Year 1, and ALC results need to indicate \geq 800 cells per microliter at the start of the Year 2 treatment course. If necessary, the Year 2 treatment course should be delayed for up to 6 months to allow for recovery of lymphocytes to \geq 800 cells per microliter. If this recovery takes more than 6 months, the patient should not receive further treatment with cladribine tablets.

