9.7.3 Statistical Methods

Descriptive statistics will be used to summarize data. If the outcome in question is a continuous variable, the number of observations, number of missing values, mean, SD, median, first quartile and third quartile, minimum and maximum values will be presented; if the outcome is categorical, numbers and percentages of patients for each of the categories and numbers and percentages of missing values will be presented.

Where appropriate, 95% CIs will be presented. For continuous data, CIs for the mean will be calculated assuming a normal distribution of the data. CIs for binary endpoints will be presented using the Clopper-Pearson method.

Time to event data will be analyzed both descriptively as continuous data and through Kaplan-Meier analysis.

Primary Endpoint Analysis:

The ARR over the 24-month period will be presented, accompanied by the respective 95% CI.

Sensitivity analyses of the ARR will be performed considering the relapses as count data and using a negative binomial regression model with time as explanatory variables. A zero-inflated negative binomial regression model will be also considered.

Secondary Endpoints Analysis:

All secondary endpoints will be analyzed at Month 12 (interim analysis) and Month 24 (final analysis). Data will be summarized descriptively.

ARR (prospective assessment): The ARR over the 12-Month and 24-Month follow-up period after starting cladribine tablets will be presented, accompanied by the respective 95% CIs.

Other relapse analyses: The proportion of patients experiencing a relapse, ARR associated with hospitalization and associated with glucocorticoid use will be presented together with the corresponding 95% CI over the 24-month and over the 12-month period.

[figure not shown]
Treatment adherence: Treatment adherence, based on modified versions of the MS-TAQ, will be described at baseline (modified for self-injectables to assess adherence during last previous

injectable DMD treatment), and for the first and second course of treatment with cladribine tablets during the first and second treatment year (modified for cladribine tablets).

Other PROs: For each ePRO score (TSQM-14, SF-36, MFIS-5, BDI-7, WPAI-MS, and PDDS), Resolution and the actual value at each visit and change in scores from baseline to Month 6, 12 and 24 will be described.

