#### **Additional Subgroup Analysis Populations**

	Analysis Population		
Analyses	Full Analysis Set	Per Protocol Analysis Set	Safety Analysis Set*
Baseline Assessments (baseline characteristics of patients initiating cladribine tablets, baseline PRO data, baseline laboratory data, baseline data on previous MS DMD use, relapses during the previous 2 years [or since MS diagnosis if diagnosis <24 months], baseline MRI data, retrospective MRI data	~	~	V
and past treatment adherence)			,
Compliance and Exposure	~		~
Primary Endpoint Analysis (ARR over the 24-month period)	$\checkmark$	$\checkmark$	~
Secondary Endpoints Analysis: The ARR over the 12-Month follow- up period , Sensitivity analyses of the ARR, ARR during the last 24 months (or since MS diagnosis if diagnosis <24 months) before starting cladribine tablets, Other relapse analyses	✓ 	~	×

	Analysis Population		
Analyses	Full Analysis Set	Per Protocol Analysis Set	Safety Analysis Set*
Treatment patterns (MS treatment during the last 2 years (or since MS diagnosis if diagnosis <24 months) before transition to cladribine tablets, concomitant treatment for MS, follow-up treatment in case of discontinuation of cladribine tablets)	~		~
PROs and treatment adherence	$\checkmark$		$\checkmark$
Analyses of MRI imaging data	✓		✓
JCV antibody status	✓		✓
Analyses of ALC as well as complete blood count and lymphocyte subsets, if available	✓	$\checkmark$	✓
Concomitant medications	✓		✓
Safety	✓		✓

Subgroup analyses will be performed for the primary endpoint on subgroups as defined below.

Subgroups:

The following subgroups will be defined:

- Patients completing the 24-month study
- Patients not completing the 24-month study (i.e., lost to follow-up, withdrawing consent, protocol deviations)
- Patients not completing treatment (i.e., completing Year 1 treatment but not Year 2 treatment, or not completing both courses of treatment each year)
- Type of MS at screening: RRMS, aSPMS, PPMS, CIS
- Patients diagnosed with MS <24 months before transitioning to cladribine tablets
- Centers
  - Pooling of centers: Because of the high number of participating centers and the anticipated small number of patients in each centers data will be pooled across centers, and the factor centers will not be considered in statistical models or for subgroup analyses.

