## 14 Efficacy Analyses

## 14.1 Primary Endpoint: ARR

## 14.1.1 Primary Objective: Analysis of the ARR

Analysis (Analysis	Derivation	Statistical Analysis Methods	Missing data handling
Population)			
Primary endp	oint: ARR over 24 Month	S	
Primary (FAS)	ARR over 24 Months. The ARR over 24 Months of a patient is calculated as the number of relapses of the patient divided by the number of days on study for that patient and multiplied by	The population estimate will be based on the average of the ARR values for the patients in the study. The corresponding 95% CI will be reported. The Statistical Analysis Software (SAS) ® MEANS procedure will be used to compute these quantities. The following descriptive statistics will be reported: mean,	Patients discontinuing early are analyzed according to number of years of follow-up on treatment and number of relapses observed at the time of discontinuation.
Secondary (PP)	365.25. This variable will be considered to get population estimates.	SD, min, max, median, first quartile (Q1) and third quartile (Q3).	
	A relapse will be defined as per routine clinical practice as determined by the investigator		
	Time on Study (days) = (Date of Study Completion or Date of study discontinuation - Date of first dose of cladribine tablets +1)		
Sensitivity (FAS)	Model based ARR, defined as expectation of relapses divided by time on study.	The estimate of the expected ARR at Month 24 will be based on a Negative Binomial (NB) model for relapse count, with offset equal to the log of years on study and adjustment for categorical number of relapses in the last 2 years, or since MS diagnosis if diagnosis <24 months (≤1 relapse, >1 relapse). The NB regression will be computed with the SAS ® GENMOD procedure, using the dist=NB option in the MODEL statement	Same handling as for the primary analysis

Analysis (Analysis Population)	Derivation	Statistical Analysis Methods	Missing data handling
		*The estimate of the expected ARR at Month 24 will be based on a Zero Inflated NB model for relapse count, with offset equal to the log of years on study and adjustment for categorical number of relapses in the last 2 years, or since MS diagnosis if diagnosis <24 months (≤1 relapse, >1 relapse). The NB regression will be computed with the SAS ® GENMOD procedure, using the dist=ZINB option in the MODEL statement.	

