## 14.1.3 Secondary Analyses of the ARR

The secondary analysis of the primary endpoint (ARR at Month 24) will be conducted on the PP population using the same method of the primary analysis.

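### The Per Protocol ARR counts relapses from first dose in patients chosen for completing the Year 2 course; if Year 1 relapsers miss that course more often than others, it is biased low

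*SAP*

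**What the plan says.** - **Who is in the set.** SAP 8.2: "The PP includes all patients who have completed a full treatment course of cladribine tablets", meaning "2 weeks of treatment [4-5 doses per week] for Years 1 and 2". Members must also be patients who "are compliant with all entry criteria and without protocol deviations".
- **When the Year 2 condition is met.** Protocol 9.2.2 places the two treatment weeks "1 at the beginning of the first month and 1 at the beginning of the second month of the respective year", and allows Year 2 to start up to 6 months late.
- **Where the ARR clock starts.** SAP 14.1.1 divides a patient's relapses by time on study, which ends at study completion or discontinuation and starts at first dose: "Date of study discontinuation - Date of first dose of cladribine tablets +1". The same derivation serves FAS and PP.
- **How PP is analysed.** SAP 14.1.3 says that the 24-month ARR "will be conducted on the PP population using the same method of the primary analysis". No landmark, later clock start or caveat is given.
- **The 12-month ARR.** The table of analyses by population in SAP 8.2 has a row beginning "Secondary Endpoints Analysis: The ARR over the 12-Month follow- up period", marked for FAS and PP. Protocol 9.7.3 starts that window at treatment: "The ARR over the 12-Month and 24-Month follow-up period after starting cladribine tablets will be presented".
- **When PP is skipped.** SAP 8.2 omits PP efficacy analyses if PP holds at least 90% of the FAS, on the ground that any difference should be negligible.

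**The concern.** Membership of the set is settled in Year 2, but the outcome is counted from the start of Year 1. A patient who relapses in Year 1 and then does not take the second course leaves the PP set and takes the relapse along. Protocol 9.2.3 keeps following such a patient, so the relapse stays in the FAS. A relapse-free patient who completes Year 2 stays in both sets. If relapse makes missing Year 2 more likely, the PP ARR falls below the FAS ARR even when completing the course has no effect on the relapse rate. A reader could then take the gap for the benefit of the full regimen.

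The 12-month PP ARR is the sharper case. None of its outcome time lies after the Year 2 event that defines the set. Only the Year 1 course condition is met inside its window.

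**Working it through.** **Timing.** The second Year 2 treatment week falls one month into Year 2: 12 + 1 = about Month 13. With the longest delay it is 13 + 6 = about Month 19. The 12-month window has closed by then. The 24-month window (30 months if Year 2 is delayed) is a little more than half over.

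**Inputs.** The documents available state no figure to reproduce: no expected ARR and no rate of missing Year 2. All rates below are assumptions.
- L: true yearly relapse rate, the same in both years and unaffected by missing Year 2.
- p1, p0: probability of missing Year 2 with and without a Year 1 relapse.
- P0: probability of no Year 1 relapse, exp(-L) under Poisson.
- Full follow-up, so that the mean of patients' ARRs (the SAP 14.1.1 estimate) equals the mean count per year.

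**Formulas.**
- PP share of FAS = (1-p0)P0 + (1-p1)(1-P0)
- PP 12-month ARR = L(1-p1) / PP share
- PP 24-month ARR = (PP 12-month ARR + L) / 2 under Poisson

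**Worked case.** L = 0.15, p1 = 40%, p0 = 15%, P0 = exp(-0.15) = 0.8607.
- Share = 0.85 × 0.8607 + 0.60 × 0.1393 = 0.815
- 12-month = 0.15 × 0.60 / 0.815 = 0.110, or -26%
- 24-month = (0.110 + 0.150) / 2 = 0.130, or -13%

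**Range.**

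| True ARR | Miss Year 2: relapsers / others | PP share | PP 12-month | PP 24-month |
|---|---|---|---|---|
| 0.15 | 50% / 15% | 80% | 0.094 (-38%) | 0.122 (-19%) |
| 0.15 | 40% / 15% | 82% | 0.110 (-26%) | 0.130 (-13%) |
| 0.15 | 25% / 10% | 88% | 0.128 (-15%) | 0.139 (-7%) |
| 0.20 | 30% / 10% | 86% | 0.162 (-19%) | 0.181 (-9%) |
| 0.20 | 30% / 5% | 90.5% | 0.155 (-23%) | 0.177 (-11%) |
| 0.20 | 10% / 5% | 94% | 0.191 (-4%) | 0.196 (-2%) |
| 0.20 | 10% / 10% | 90% | 0.200 (0%) | 0.200 (0%) |
| 0.20 | 10% / 30% | 74% | 0.244 (+22%) | 0.222 (+11%) |

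Simulation with 2,000,000 patients agreed to about 0.001 in the cases tried, among them the 30% / 10% row.

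**The 90% rule.** The share above counts only missed Year 2 courses; entry-criteria failures and deviations would lower it. The rule would suppress the 10% / 5% case, where the difference is small. It would also suppress the 30% / 5% case, where PP and FAS differ by -23% and -11%. A share of 90% therefore does not show that the difference is negligible.

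**Counting only after selection** (approximated as Year 2 only; L = 0.20, 30% / 10%). Let patients' rates vary, with negative binomial counts of shape k, so P0 = (k/(k+L))^k. Smaller k means more variation.

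| Model | From first dose, 24-month | Year 2 only |
|---|---|---|
| Poisson | 0.181 (-9%) | 0.200 (0%) |
| k = 1 | 0.178 (-11%) | 0.194 (-3%) |
| k = 0.5 | 0.175 (-13%) | 0.189 (-6%) |

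The landmark removes the direct selection on the counted relapses. What remains is that completers have lower underlying rates. With 50% / 10% at the same L, the remainder is -7% (k = 1) and -12% (k = 0.5).

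**The case against.** **The direction is not documented.** This stands. The specific reasons that the protocol lists for withholding or stopping a course (lymphocytes not recovered in Protocol 9.2.2; pregnancy, infection or renal impairment in 11.4) have no stated link to relapse. Protocol 7.3 says that most DMDs are continued unless ineffective or not tolerated. That makes relapse-related switching plausible, but it describes drugs taken indefinitely, not a planned two-course regimen. A reader might infer that the PP ARR must look better than the FAS ARR whatever the drug does. The documents do not support that: equal rates give no bias, and reversed rates give an upward one.

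**Immortal time is too strong a name.** This stands. A Year 1 relapse does not bar a patient from PP. A relapser who takes Year 2 is included and the relapse counts. The problem is selection on a post-baseline event.

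**The 12-month limb has thin support.** Partly right. It rests on one table row that bundles several analyses. SAP 14.1.1 and 14.1.3 assign PP only to the 24-month ARR, and 14.1.1 gives the sensitivity models in that same row to the FAS alone. SAP 5 sends the 12-month ARR to Section 14.2, which is blacked out in the public copy and may qualify it. The table is still current text and marks PP, so it needs correcting or confirming.

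**The shift is within sampling error.** In the worked case the 24-month shift is 0.02. Under Poisson the 95% half-width is 1.96 × sqrt(0.15 / 2N): 0.076, 0.054 and 0.038 for assumed N of 50, 100 and 200. True, but an interval around a biased estimate does not show the bias.

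**The definition already discloses the condition, and PP is secondary.** SAP 8.2 does say that both courses must be completed, and 14.1.4 plans ARR by treatment completion. Neither warns that relapses before the selection are counted.

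**Conclusion.** The structural point holds on the text alone: the PP set is fixed at about Month 13 to 19 and its ARR is counted from first dose. Whether this produces bias, and in which direction, depends on whether Year 1 relapsers miss the Year 2 course more often than other patients. If they do, the PP ARR is biased low. In the adverse scenarios tabulated this runs from -4% to -38% at 12 months and from -2% to -19% at 24 months. These sizes rest on assumed rates, a constant relapse rate and Poisson counts.

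A reader might carry the problem over to the main result. The documents do not support that: the primary analysis uses the FAS, which keeps patients who stop treatment, and it is unaffected. The point concerns a supportive descriptive analysis. It is worth correcting because the fix is cheap and the misreading is easy.

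**What to change.** 1. **12-month ARR.** In the SAP 8.2 table, remove the PP mark for this analysis, or define PP for it on the Year 1 course only. Align the row with SAP 14.1.1 and 14.1.3.
2. **24-month PP ARR.** Keep it from first dose, but report it as the rate among patients who went on to complete both courses, not as the effect of the full regimen. The treatment-completion subgroups in SAP 14.1.4 need the same label.
3. **Landmark PP ARR.** Add an analysis counting relapses and time from completion of the second Year 2 treatment week to the end of follow-up. Starting at the first Year 2 dose would leave about a month before the set is fully selected.

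**Cost.** SAP wording and one more derived start date. Protocol 9.3 already collects treatment start and stop dates and relapse onset dates. The landmark result covers about 11 months per patient (24 - 13, or 30 - 19 if delayed) and estimates a Year 2 rate, so it supplements the 24-month PP figure and does not replace it. Two limits remain. The case-mix difference stays (about -3% to -6% at 30% / 10% and ARR 0.20, more with a wider gap). The no-deviation condition also has no time limit, so deviations after the landmark would still select patients unless the SAP counts them only up to that date.
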